8.2.4. Other Analyses

8.2.4.1. Analysis of Healthcare Resources and Costs

Analysis of Healthcare Resources and Costs will be based on the Full Analysis Set.

The number of visits (since the last study visit) to a rheumatologist or other RA specialist will be summarised for each time-point.

The number of patients with diagnostic tests and the number of diagnostic tests (since the last study visit) will be summarised at each time-point by type of test (WBC, ESR/CRP, Glucose, Hepatic enzymes, Urea, Creatinine, lipid profile, X-rays, other) and overall.

The number of patients who are hospitalised, the number of hospitalisations (since the last study visit) per patient and the number of days hospitalised per patient will be summarised overall and by type of hospitalisation (day care or overnight stay) for each time-point. The reason for hospitalisation will also be summarised.

The above summaries will all be produced using the methods outlined in [Section 8.1.3](#).

The summaries of healthcare resources will be produced by the following subgroups:

- Education Status;
- Working Status;
- Disease Severity;
- Treatment;
- Co-morbidities; HAQ-DI at baseline; EQ-5D at baseline.

See [Section 5.3](#) for more detail on the subgroups.

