9.4.1. Study Procedures

Consecutive subjects attending will be included if they fulfil all selection criteria for the study and are started on treatment with tofacitinib for moderate to severely active rheumatoid arthritis.

All visits shall be scheduled according to clinical practice. Within this study 4 visits may be documented and one follow-up telephone communication at least 28 days after the last clinic visit for those patients with an ongoing treatment-related AE should be conducted. At each visit subjects will undergo procedures in compliance with the country label and as per standard of care. In order to collect comparable study data, visits occurring +/- 14 days of the scheduled visit date can be documented. If a patient misses one or more pre-planned study visits the patient can remain in the study.

After a training session the sites will get access to the eDCT where the data and findings of the patient are documented. Also a folder with questionnaires will be provided. The collection of all data is prospective. Dose and duration of treatment should be based on clinical and individual needs and are determined by the treating physician. To provide accurate information of the treatment, the initial tofacitinib dose and all changes and the reasons for changes are documented during the course of the evaluation. The concomitant medication is determined by the treating physician and is registered in the eDCT.

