9.4.29. Diagnostic Tests

The number and type of diagnostic tests performed since the last visit will be documented at visits 2-4.

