8.1.3. Analysis of Categorical Data

Unless specified otherwise, categorical variables will be summarised using counts and percentages. Percentages will be based on the number of patients with non-missing data at each visit.

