11. APPENDICES

11.1. APPENDIX 1: DATA DERIVATION DETAILS

A1.1 Definition and use of visit windows in reporting

Visit windows will be used for efficacy variables, and for any safety displays that display by month.

Visit Label	Target Day	Definition [Day window]
Enrolment	1	Day 1 or before
Month 3	91	Day 2 to 137
Month 6	183	Day 138 to Day 274
Month 12	365	Day 275 onwards

If two or more visits fall into the same window, keep the one closest to the Target Day. If two visits are equal distance from the Target Day in absolute value, the later visit should be used.

(Safety analysis may follow Pfizer standard).

A1.2 Definitions of bDMARDs and csDMARDs

The following drug names will be used to determine whether drugs are bDMARDs or csDMARDs

List of bDMARD (Brand name should be used to be able to track biosimilars)

[figure not shown]
Humira (Adalimumab)

Cimzia (Certolizumab Pegol)
Enbrel (Etanercept)
Simponi (Golimumab)
Remicade (Infliximab)
Orencia (Abatacept)
Roactemra (Tocilizumab)
Kineret (Anakinra)
Mabthera (Rituximab)
Benepali (Etanercept)
Inflectra (Infliximab)
Other

List of csDMARD

Methotrexate
Leflunomide
Hydroxychloroquine sulfate
Sulfasalazine
Other

CCI

PFIZER CONFIDENTIAL

Final Version 1.0

28-Jan-2020

Page 36 of 36

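### Resource use is tabulated as raw counts over intervals of 90, 92 and 182 days, by categorical methods and with no time denominator, so the Month 3, 6 and 12 figures are not comparable

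*SAP*

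**What the plan says.** SAP Sections 6.3.1 and 8.2.4.1 define each resource item by what has happened since the previous study visit. For specialist consultations: "The number of visits (since the last study visit) to a rheumatologist or other RA specialist will be summarised for each time-point". For admissions: "the number of hospitalisations (since the last study visit) per patient and the number of days hospitalised per patient will be summarised overall", and also by type of admission. Diagnostic tests follow the same pattern, matching how they are collected under Protocol Section 9.4.29: "The number and type of diagnostic tests performed since the last visit will be documented at visits 2-4". Those visits are Months 3, 6 and 12.

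On method, SAP Section 8.2.4.1 says "The above summaries will all be produced using the methods outlined in" Section 8.1.3. That section reads: "categorical variables will be summarised using counts and percentages. Percentages will be based on the number of patients with non-missing data at each visit". The mean, SD, median and range are in Section 8.1.2, which is not invoked for any resource item.

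On attendance, Protocol Section 9.4.1 says "If a patient misses one or more pre-planned study visits the patient can remain in the study". Neither document gives a person-time denominator, an annualised rate, a cumulative 12-month figure, or a rule for the longer interval that follows a missed visit.

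**The concern.** Two things do not fit the quantity being measured.

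First, a count since the last visit depends on how long ago that visit was. The last scheduled interval is about twice as long as each of the first two, and any interval grows when the preceding visit was missed. The percentages in Section 8.1.3 are based on the number of patients with data, not on time observed. Figures placed side by side for Months 3, 6 and 12 therefore cover different lengths of time, and nothing in the table adjusts for it.

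Second, consultations, tests, admissions and days in hospital are numeric. Section 8.1.3 offers only counts and percentages of categories, so the SAP does not call for a mean or a measure of spread for them, although Section 8.2.4.1 itself describes some of them per patient.

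Estimating resource use and costs in Greece is a stated secondary objective (Protocol Section 8) and a listed key secondary endpoint (Protocol Section 8.1.2, item k). At stake is whether a reader of these tables can tell stable use from rising use.

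**Working it through.** **Inputs**
- Target days 1, 91, 183 and 365: SAP Appendix 1, A1.1.
- Visit tolerance of 14 days either side, and permission to stay in the study after missed visits: Protocol Section 9.4.1.
- Event rate: not given in either document. Assumed constant over time, with a range of 0.1 to 12 events per patient-year.
- For the percentage of patients with any event: Poisson counts assumed. A year is 365.25 days.

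The documents state no figure for resource use, so there is none to reproduce.

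**Step 1. Interval lengths, all visits attended on target**
- Month 3: 91 − 1 = 90 days
- Month 6: 183 − 91 = 92 days
- Month 12: 365 − 183 = 182 days

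Ratios: 182/90 = 2.02 and 182/92 = 1.98. The 14-day tolerance does not remove the gap. The Month 6 interval then runs from 169 − 105 = 64 to 197 − 77 = 120 days, and the Month 12 interval from 351 − 197 = 154 to 379 − 169 = 210 days, so the ranges do not overlap. The SAP's reporting windows are wider still (Month 6 is "Day 138 to Day 274"), so they do not standardise the interval.

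**Step 2. What a constant rate would look like**

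Mean count = r × interval / 365.25. Proportion with at least one event = 1 − exp(−mean count).

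| Assumed rate per patient-year | Mean count, Months 3 / 6 / 12 | % with any event, Months 3 / 6 / 12 | Ratio of %, Month 12 to Month 6 |
|---|---|---|---|
| 0.1 | 0.025 / 0.025 / 0.050 | 2.4 / 2.5 / 4.9 | 1.95 |
| 0.3 | 0.074 / 0.076 / 0.149 | 7.1 / 7.3 / 13.9 | 1.91 |
| 1 | 0.246 / 0.252 / 0.498 | 21.8 / 22.3 / 39.2 | 1.76 |
| 4 | 0.986 / 1.008 / 1.993 | 62.7 / 63.5 / 86.4 | 1.36 |
| 12 | 2.957 / 3.023 / 5.979 | 94.8 / 95.1 / 99.7 | 1.05 |

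Mean counts roughly double at Month 12 whatever the rate. With the same patients at each visit, totals do too. The percentage with any event rises by a factor between 1 and 2, nearer 2 for rare events and nearer 1 for frequent ones.

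**Step 3. Missed visits**
- Month 6 missed: the Month 12 interval is 365 − 91 = 274 days, which is 274/92 = 2.98 times a 92-day interval and 274/182 = 1.51 times the scheduled Month 12 interval.
- Months 3 and 6 both missed: 365 − 1 = 364 days, which is 364/92 = 3.96 times a 92-day interval.
- Total time covered: 90 + 92 + 182 = 364 days with full attendance and 90 + 274 = 364 days with Month 6 missed. Events move to a later time-point; the 12-month total does not change.

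**Step 4. The same data with a time denominator**

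At 4 events per patient-year the raw means are 0.99, 1.01 and 1.99. Dividing each by its interval (for Month 12, 1.993 / 182 × 365.25) gives 4.0, 4.0 and 4.0. The artefact disappears.

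**The case against.** The case for leaving the text alone has real content.

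- **The objective is descriptive.** SAP Section 2.4 makes secondary objectives descriptive unless otherwise stated, and Section 4 sets no formal hypotheses. No test of change in resource use is planned, and the recall period is disclosed in the definition of each item. This stands and limits the consequence. It does not make the columns comparable, and a reader cannot correct for individual missed visits from the published table.
- **Counts are discrete, so counts and percentages are legitimate.** Protocol Section 9.7 does assign discrete variables to that format, and a complete frequency table lets a reader rebuild a mean or total. It does not let the reader rebuild a rate, because the days observed are not shown.
- **The economic evaluation lies outside this SAP, and the table shells are in a separate document.** Both are true (SAP Sections 6.3.1 and 9). A reader might infer that costing cannot be done from this plan. The documents do not support that: costing can draw on the patient-level records, and the economic plan is not available to judge. The resource-use summaries are nevertheless in this SAP, and its text sends them to Section 8.1.3.
- **Missed visits do not inflate overall use.** A reader might infer that subgroups with more missed visits would look costlier overall. Step 3 shows they would not over 12 months. Within a time-point the nominal interval is the same for every subgroup, and nothing in the documents suggests that attendance differs between them. Only a single time-point's figure can shift.

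**Conclusion.** The concern holds in a conditional form. SAP Section 8.2.4.1 prescribes raw counts over unequal intervals and sends numeric items to a categorical method. At a constant underlying rate, mean or total counts at Month 12 would be about twice those at Months 3 and 6 (2.02 and 1.98 by target day). The percentage of patients with any event would be 1.05 to 1.95 times its Month 6 value across the assumed range of rates.

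A reader might infer that reported use must double at Month 12 regardless. It need not: the doubling applies to means and totals, and rests on a constant rate and visits attended on target. The documents give no rate. Nor do they support a figure for the extra rise in the Month 12 mean from missed visits: they give no missed-visit proportion, and Protocol Section 9.5 expects missing data to be minimal, although Section 9.9 accepts that missing items are more likely in usual care.

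The effect is confined to a descriptive secondary objective. The primary analysis is untouched.

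**What to change.** Amend SAP Section 8.2.4.1 as follows:

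1. Summarise consultations, diagnostic tests, admissions and hospital days with the descriptive statistics of Section 8.1.2.
2. At each time-point, also report these items per patient-year, using each patient's actual days since the last attended visit. Total events divided by total days is more stable than averaging individual ratios when some intervals are short.
3. Add a cumulative figure over follow-up per patient-year, which is unaffected by events moving between time-points after a missed visit.
4. Keep Section 8.1.3 for yes/no items (any test, any admission) and for reasons for admission, and state the interval length beside those percentages.

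The cost is SAP wording and matching table shells. No new data are needed: visit dates are already required to apply the day windows in Appendix 1.

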8.2.5. Summary of Analyses

Outcome	Analysis Set	Supports Protocol Objective Number	Subgroups	Statistical Method	Covariates/ Strata	Missing Data
Rate of Remission at Month 6	FAS	1	None	Logistic regression	Potential predictive factors outlined in Section 6.4	NRI
Rate of LDA at Month 6	FAS	1	None	Logistic regression	Potential predictive factors outlined in Section 6.4	NRI
Rate of Remission at Month 12	FAS	2	None	Logistic regression	Potential predictive factors outlined in Section 6.4	NRI
Rate of LDA at Month 12	FAS	2	None	Logistic regression	Potential predictive factors outlined in Section 6.4	NRI
EQ-5D	FAS	2	None	MMRM	Baseline score, timepoint fitted as a fixed effect and baseline by timepint interaction	MMRM
FACIT-Fatigue	FAS	2	None	MMRM	Baseline score, timepoint fitted as a fixed effect and baseline by timepint interaction	MMRM
WPAI	FAS	2	None	MMRM	Baseline score, timepoint fitted as a fixed effect and baseline by timepint interaction	MMRM

PFIZER CONFIDENTIAL

Final Version 1.0

28-Jan-2020

Page 33 of 36

9. LIST OF TABLES AND TABLE SHELLS

A list of tables (LOT) will be produced and will be provided in a separate document.

11. APPENDICES

11.1. APPENDIX 1: DATA DERIVATION DETAILS

A1.1 Definition and use of visit windows in reporting

Visit windows will be used for efficacy variables, and for any safety displays that display by month.

Visit Label	Target Day	Definition [Day window]
Enrolment	1	Day 1 or before
Month 3	91	Day 2 to 137
Month 6	183	Day 138 to Day 274
Month 12	365	Day 275 onwards

If two or more visits fall into the same window, keep the one closest to the Target Day. If two visits are equal distance from the Target Day in absolute value, the later visit should be used.

(Safety analysis may follow Pfizer standard).

A1.2 Definitions of bDMARDs and csDMARDs

The following drug names will be used to determine whether drugs are bDMARDs or csDMARDs

List of bDMARD (Brand name should be used to be able to track biosimilars)

[figure not shown]
Humira (Adalimumab)

Cimzia (Certolizumab Pegol)
Enbrel (Etanercept)
Simponi (Golimumab)
Remicade (Infliximab)
Orencia (Abatacept)
Roactemra (Tocilizumab)
Kineret (Anakinra)
Mabthera (Rituximab)
Benepali (Etanercept)
Inflectra (Infliximab)
Other

List of csDMARD

Methotrexate
Leflunomide
Hydroxychloroquine sulfate
Sulfasalazine
Other

CCI

PFIZER CONFIDENTIAL

Final Version 1.0

28-Jan-2020

Page 36 of 36

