9.4.3. Schedule of Activities

The schedule of activities table provides an overview of the visits that may be documented. Refer to the **STUDY PROCEDURES** and **ASSESSMENTS** sections of the protocol for detailed information on each documentation and assessment.

According to his clinical practice the investigator may schedule visits (unplanned visits) in addition to those listed on the schedule of activities (SOA), in order to conduct evaluations or assessments required to protect the well-being of the subject. As this is a non-interventional study none of these visits are mandatory and every visit should be scheduled according to clinical practice.

Table 5. Schedule of Activities

Study Week	Baseline (Enrollment)	Month 3	Month 6	Month 12
Visit Number	1	2	3	4
Informed Consent	x			
Anamnesis/Medical History	x			
Demographic data	x			
Educational level	x			
Working status	x			x
Inclusion/exclusion criteria	x			
Vaccination status	x			
Treatment/Medication				
Prior RA drug treatment	x			
Concomitant RA drug treatment	x	x	x	x
Co-medication	x	x	x	x
Safety				
Inflammatory markers	x	x	x	x
Documentation of Comorbidities	x			
Documentation of AE		x	x	x
Efficacy				
Number of swollen and tender joints	x	x	x	x
Morning stiffness	x	x	x	x
Patients Global Assessment of Arthritis	x	x	x	x
Physicians Global Assessment of Arthritis	x	x	x	x
Patient Assessment of Arthritis Pain	x	x	x	x
Health Assessment Questionnaire – Disability Index (HAQ-DI)	x	x	x	x

Study Week	Baseline (Enrollment)	Month 3	Month 6	Month 12
Visit Number	1	2	3	4
EuroQol EQ-5D Health State Profile	x	x	x	x
Work Productivity and Activity Impairment (WPAI) Questionnaire	x	x	x	x
FACIT (Functional Assessment of Chronic Illness Therapy) – Fatigue	x	x	x	x
Overall satisfaction with treatment	x			x
Medical visits		x	x	x
Diagnostic tests		x	x	x
Hospitalizations		x	x	x

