7. HANDLING OF MISSING VALUES

For the primary endpoints of remission and LDA, a non-responder imputation (NRI) will be used for patients who have all components of DAS28-4 (CRP) missing at Month 6. This means that if a patient has all components of the DAS28 (CRP) missing at Month 6, they will be classified as a non-responder (i.e. not having remission or LDA respectively) for the purposes of the primary analyses. If a patient has at least one non-missing component of the DAS28-4 (CRP) at Month 6, then missing components will be imputed by carrying forward the last non-missing post-baseline value, before deriving the DAS28-4 (CRP) at Month 6 in order to determine whether they have achieved remission or LDA at Month 6.

For EQ-5D, FACIT-Fatigue Scale and WPAI, missing data will be handled using

the mixed-effect model as described in [Section 8.1.2](#). In addition, the methods for handling missing data when deriving these scores described below will also be applied.

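### SAP A1.1 picks one visit per window by date alone, so if an extra or off-schedule visit is recorded, a measured Month 6 DAS28-4 (CRP) can give way to an imputed result

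*SAP*

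**What the plan says.** - SAP Appendix A1.1 sets the scope: "Visit windows will be used for efficacy variables, and for any safety displays that display by month". DAS28-4 (CRP) is therefore covered. The Month 6 window is "Day 138 to Day 274" with target Day 183; Month 12 runs from Day 275 with no upper limit.
- The selection rule is "If two or more visits fall into the same window, keep the one closest to the Target Day", and the tie-break is "If two visits are equal distance from the Target Day in absolute value, the later visit should be used". Neither sentence refers to what the visit contains, and nothing elsewhere in the SAP adds such a condition.
- SAP Section 7 then acts on what is missing at Month 6. With nothing available, "if a patient has all components of the DAS28 (CRP) missing at Month 6, they will be classified as a non-responder". With at least one component present, "missing components will be imputed by carrying forward the last non-missing post-baseline value".
- SAP 8.2.3.2 analyses Month 12 remission and LDA in a similar way, and SAP 8.2.5 lists non-responder imputation for them. Section 7 itself names only Month 6, so component carry-forward at Month 12 is an inference.
- On visits, Protocol 9.4.1 says that "visits occurring +/- 14 days of the scheduled visit date can be documented", and 9.4.2 plans up to four documented visits. Protocol 9.4.3 also allows unplanned visits under clinical practice. Protocol 9.9 expects single items, such as CRP, to be missing.

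**The concern.** The rule selects whole visits and the imputation works on what the selected visit lacks. Between the two, no step asks whether the missing item was measured at another visit in the same window. A patient fully assessed in the Month 6 window can thus be treated as having no Month 6 data. Protocol 9.7.3.1 reserves non-responder imputation for patients whose Month 6 data are missing; here the selection rule would create the missingness.

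The primary endpoints are at stake. When the kept visit is empty, the error runs one way only, from responder to non-responder. When it is partly complete, an older value can move the score across 3.2 or 2.6 in either direction. Protocol 9.4.3 links unplanned visits to the subject's well-being, so extra visits may be more common in sicker patients. That is an inference, but if it holds, the misclassification would be related to the baseline severity factors under test as predictors.

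**Working it through.** **Inputs.** Windows, target days and the selection rule are from SAP A1.1; imputation is from SAP 7; the DAS28-4 (CRP) formula is from SAP 6.1.1; the 14-day tolerance is from Protocol 9.4.1; the 50% LDA rate, ten covariates and N = 10k/p are from Protocol 9.5.

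**1. The plan's own figure.** N = 10 × 10 / 0.50 = 200 patients, with 200 × 0.50 = 100 events. It reproduces, and this point does not challenge it. Protocol 9.5 makes no allowance for missing data.

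**2. When two visits can share a window.** Taking the SAP target days as the scheduled dates:

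| Visit | Target ± 14 days | SAP window | Inside? |
|---|---|---|---|
| Month 3 | Day 77–105 | Day 2–137 | yes |
| Month 6 | Day 169–197 | Day 138–274 | yes |
| Month 12 | Day 351–379 | Day 275 onwards | yes |

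On-schedule visits fall one per window. Two share the Month 6 window (274 − 138 + 1 = 137 days) only if an additional or out-of-tolerance visit is recorded. The rule in A1.1 exists for that case.

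**3. Kept visit empty (illustrative).** Day 180 has no component; Day 192 is complete. The distances are |180 − 183| = 3 and |192 − 183| = 9 days, so Day 180 is kept. All components are missing and the patient is a non-responder whatever Day 192 showed.

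**4. Kept visit partly complete, discarded visit later (illustrative).** Day 183 has TJC 1, SJC 1, PtGA 20 mm and no CRP. Day 200 has the same values and CRP 4 mg/L. Month 3 CRP was 25 mg/L.

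- With the measured CRP: 0.56·√1 + 0.28·√1 + 0.36·ln(4 + 1) + 0.014·20 + 0.96 = 2.66, which is LDA.
- With the carried-forward CRP: 0.56 + 0.28 + 0.36·ln(25 + 1) + 0.28 + 0.96 = 3.25, which is not LDA.

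Day 183 is kept. Day 200 comes later, so it cannot be carried forward, and the patient changes category.

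**5. Discarded visit earlier.** Section 7 does not say whether an unselected visit may supply a carried-forward value. If it may, a partly complete kept visit is rescued. An empty kept visit is not, because non-response applies as soon as all components are missing.

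**6. Size.** One responder lost is 1/200 = 0.5 percentage points and 1/10 = 0.1 events per variable. The share affected is not in the documents. The table **assumes** a share, that half of those affected are in LDA, and that every kept visit is wholly empty. The last assumption makes each row the high end for its share.

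| Assumed share of 200 | Patients | Responders lost | Events | LDA rate | Events per variable |
|---|---|---|---|---|---|
| 1% | 2 | 1 | 99 | 49.5% | 9.9 |
| 2% | 4 | 2 | 98 | 49.0% | 9.8 |
| 5% | 10 | 5 | 95 | 47.5% | 9.5 |
| 10% | 20 | 10 | 90 | 45.0% | 9.0 |

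**The case against.** The strongest reply is that the situation lies outside the planned schedule. At most four visits are to be documented, and joint counts, inflammatory markers and PtGA are scheduled at each. The follow-up telephone call is listed separately from those visits. The protocol allows unplanned visits but does not say that they are entered as assessment visits. Much of this stands: it makes the problem uncommon. It does not remove it, because A1.1 itself provides for several visits in a window and Protocol 9.9 expects incomplete ones.

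A second reply is that windows applied to efficacy variables could be read per variable, so that a record without the variable is never a candidate. That reading is possible, but the selection sentences speak of visits. A primary endpoint should not depend on which reading the programmer takes.

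Three stronger readings are tempting, and the documents do not support them:

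- *That a definite number of responders will be lost.* No frequency is given, and not every affected patient would be empty at the kept visit. Partly complete visits go to carry-forward, and some of those patients would keep their category.
- *That observed data are replaced by imputed data for every efficacy variable.* EQ-5D, FACIT-Fatigue and WPAI have neither non-responder imputation nor carry-forward across visits. For them a discarded visit means a lost observation that the MMRM treats as missing at random.
- *That Section 7 never rescues a discarded visit.* If that visit is earlier and the kept one partly complete, it might.

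**Conclusion.** The point holds as a defect in a stated rule. Followed as written, A1.1 and Section 7 together can replace a DAS28-4 (CRP) or component measured inside the Month 6 window by non-response or by an older value, and the same selection gap exists at Month 12. It needs an additional or out-of-tolerance recorded visit and is probably uncommon. The only size that follows without an assumed frequency is 0.5 percentage points of LDA rate, and 0.1 events per variable, for each responder lost among 200 patients. The effect on any predictor estimate cannot be worked out from the documents. The correction is still worth making: it is short, it concerns the primary endpoints, and the sample size has no slack for avoidable missing data.

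**What to change.** Amend SAP A1.1 and add a cross-reference in Section 7:

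1. Apply the window per efficacy variable to non-missing records. For DAS28-4 (CRP), only visits with at least one component are candidates, so an empty visit is never selected over one that has data. Among candidates, keep the existing closest-to-target and later-if-tied rules.
2. If the selected visit is only partly complete, take each missing component from the nearest other visit in the same window, preferably within a stated distance of the target day, before carrying anything forward from an earlier window.
3. Apply non-responder imputation only when no visit in the window has any component.
4. State that the same rules apply at Month 12.

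Simply preferring the nearest visit with a complete score would be worse. It could pass over a Day 183 visit lacking only CRP in favour of a complete Day 270 visit, moving the whole Month 6 assessment by 270 − 183 = 87 days. Filling by component within a distance limit avoids that.

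The cost is a few sentences in the SAP and per-variable selection in the analysis dataset. For a few patients, components of one score, or different endpoints, will come from different dates; a listing of those patients would make this visible.
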